11.9 Withdrawal Criteria for an Individual Subject

An individual patient will be withdrawn from the study for any of the following:

- An individual patient's decision. (The investigator should attempt to determine the reason for the patient's decision.)
- Non-compliance with study procedures to the extent that it is potentially harmful to the patient or to the integrity of the study data.
- A patient permanently loses capacity to provide informed consent.
- The investigator determines that continued participation in the study would not be in the best interest of the patient.

Patients who have withdrawn from the study before Day 14 will be replaced. If a patient is replaced, then all of their data will still be included for the safety assessment.

11.10 Safety Oversight

11.10.1 Safety Monitoring Committee

An independent safety monitoring committee (SMC) consisting of 3 individuals will review the study prior to initiation and then after 3 subjects have been on study drug for approximately 3 weeks. The SMC will then specify the next meeting point. The SMC will focus on subject safety and will include subject matter experts. The independent experts do not have direct involvement in the conduct of the study and have no significant conflicts of interest as defined by NIAID policy.

Prior to each SMC review, the PI will submit data as requested by the SMC. After each SMC review, a recommendation as to whether the study is to continue, be modified, or be terminated will be provided in a summary report. All SAEs, all UPs, and all IND Safety Reports will be reported by the PI to the SMC at the same time they are submitted to the IRB or IND sponsor. The SMC will be notified immediately if pausing, stopping, or halting rules are met, and the SMC will provide a recommendation for continuation, modification, or termination of the study. The PI will submit the written SMC summary reports with recommendations to the IRB.

12 Clinical Monitoring Structure

12.1 Site Monitoring Plan

An initiation meeting will be conducted by Matinas Biopharma Nanotechnologies, Inc. or an approved representative. At this meeting, the protocol and data collection procedures will be reviewed with the PI and all study staff.

Monitoring visits will be conducted during the study by Matinas Biopharma Nanotechnologies, Inc. or designee. The PI will make a reasonable amount of time available to the CRA on reasonable notice to assist with monitoring.

At each visit, the CRA will review CRIMSON data abstracts and source documents to ensure that all items have been completed and that the data provided are accurate and obtained in the manner specified in the protocol.

As per ICH-GCP 5.18 and FDA 21 CFR 312.50 clinical protocols are required to be adequately monitored. At the request of the NIAID Clinical Director this protocol monitoring for the NIH site will be conducted according to the "NIAID Intramural Clinical Monitoring Guidelines." Monitors under contract to the NIAID/OCRPRO will visit the NIH site to monitor aspects of the study in accordance with the appropriate regulations and the approved protocol. The objectives of a monitoring visit will be: 1) to verify the existence of signed informed consent documents and documentation of the ICF process for each monitored subject; 2) to verify the prompt and accurate recording of all monitored data points, and prompt reporting of all SAEs; 3) to compare abstracted information from CRIMSON data abstracts with individual subjects'

records and source documents (subjects' charts, laboratory analyses and test results, physicians' progress notes, nurses' notes, and any other relevant original subject information); and 4) to help ensure investigators are in compliance with the protocol. The monitors also will inspect the clinical site regulatory files to ensure that regulatory requirements (Office for Human Research Protections-OHRP), FDA, and applicable guidelines (ICH-GCP) are being followed. During the monitoring visits, the investigator (and/or designee) and other study personnel will be available to discuss the study progress and monitoring visit.

The investigator (and/or designee) will make study documents (e.g., consent forms, CRIMSON data abstracts and pertinent hospital or clinical records readily available for inspection by the local IRB, FDA, the site monitors, and the NIAID staff for confirmation of the study data.

A specific protocol monitoring plan will be discussed with the Principal Investigator and study staff. The plan will outline the frequency of monitoring visits based on such factors as study enrollment, data collection status and regulatory obligations.

12.2 Auditing Procedures

In addition to the monitoring visits outlined above, an investigational site may undergo a quality assurance audit. Matinas Biopharma Nanotechnologies, Inc., its authorized representative, or a regulatory agency such as the FDA may conduct the audit. If a regulatory agency requests an audit of the study site, the Investigator is required to inform Matinas Biopharma Nanotechnologies, Inc. immediately.

13 Statistical Considerations

13.1 Study Hypotheses

CAMB will improve clinical symptoms of mucocutaneous candidiasis (OC/EC/VVC) in patients that are refractory or intolerant to standard non-Page 56 of 101 intravenous therapies.

13.2 Sample Size Justification

Sixteen patients will be accrued to the study. This sample size will provide 80% power to distinguish between true underlying improvement in clinical symptom rates of 5% and 25% using a 0.043 significance level. The 0.043 type I error rate will be used since the small sample size and yes/no endpoint do not allow for a 0.05 level test. The 0.043 level is as close to 0.05 as possible without being larger than 0.05.

The 5% rate with standard of care is based on historical observations at the clinical center that in this immune deficient population few if any patients have sustained improvement.

With 16 patients there will be a probability of 0.8 (80% power) of observing 3 or more responses if the true response rate with CAMB treatment is 25%. There will be a 0.043 (type I error rate) probability of observing 3 or more responses if the true response rate with CAMB is 5% (no better than current treatments).

Analysis Populations

The safety population will comprise all subjects who received at least one dose of investigational product.

13.3 Description of the Analyses

13.3.1 Efficacy Statistical Analysis

If 3 or more clinical improvements in symptoms are observed out of the 16 patients we will conclude there is promising evidence to continue studying CAMB. With this criteria there is a 0.043 probability of concluding CAMB is promising when the true rate of clinical improvement is 5% (no better than current treatments) and there is an 0.8 probability of concluding CAMB is promising when the true rate is 25% (improvement over current treatments).

If extra patients (up to the maximum of 20 patients) are accrued to the study the data will be analyzed to maintain type I error rate less than 0.05.

13.3.2 Safety Analysis

Safety analyses will include where appropriate, descriptive statistics, counts, and percentages.

Adverse Events

AEs will be coded using Medical Dictionary for Regulatory Activities (MedDRA) and summarized by System Organ Class (SOC) and Preferred Term for each treatment group. All AEs will be captured after the first dose through the final visit or ET visit.

AEs will be summarized by presenting:

- The number and percentage of subjects experiencing any AE
- The number and percentage of subjects experiencing any AE by SOC
- The number and percentage of subjects experiencing any SAE
- The number and percentage of subjects experiencing any AE associated with study discontinuation

Clinical Laboratory Parameters

Clinical laboratory measurements (serum creatinine, potassium, CRP, ALT, AST) and changes from baseline to end-of-treatment will be summarized descriptively for each visit with the mean, median, standard deviation (SD), minimum, and maximum, by treatment group.

Vital Signs

Vital signs will be summarized descriptively for the mean, median, SD, minimum, and maximum by treatment group.

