The protocol, informed consent form(s), recruitment materials, and all participant materials will be submitted to the Institutional Review Board (IRB) for review and approval. Approval of both the protocol and the consent form must be obtained before any participant is enrolled. Any amendment to the protocol will require review and approval by the IRB before the changes are implemented to the study. In addition, all changes to the consent form will be IRB-approved; an IRB determination will be made regarding whether a new consent needs to be obtained from participants who provided consent, using a previously approved consent form.

List of Abbreviations

AE	Adverse Event		
ALP	Alkaline Phosphatase		
ALT	Alanine Transaminase		
AMB	Amphotericin B		
APECED	Autoimmune Polyendocrinopathy-Candidiasis-Ectodermal		
	Dystrophy		
AST	Aspartate Transaminase		
AUC	Area Under the Concentration vs. Time Curve		
AUC ₀₋₂₄	Area Under the Concentration vs. Time Curve from Time Zero		
	to 24 Hours Postdose		
BID	Twice Daily		
CAMB	Cochleate Oral Amphotericin B		
CFR	Code Of Federal Regulations		
C _{max}	Maximum Plasma Concentration		
CMC	Chronic Mucocutaneous Candidiasis		
CRF	Case Report Form		
CRP	C-Reactive Protein		
CRIMSON	Clinical Research Information Management System of the		
	NIAID		
DAMB	Deoxycholate Solubilized Amphotericin B		
DCR	Division of Clinical Research		

DSMB	Data and Safety Monitoring Board		
EC	Esophageal Candidiasis		
ESR	Erythrocyte Sedimentation Rate		
FDA	Food and Drug Administration		
GCP	Good Clinical Practice		
GFR	Glomerular Filtration Rate		
GI	Gastrointestinal		
HRPP	Human Research Protection Program		
ICH			
	Requirements for Pharmaceuticals for Human Use		
IND	Investigational New Drug		
IP	Intraperitoneal		
IRB	Institutional Review Board		
IUD	Intrauterine Device		
LCIM	Laboratory of Clinical Immunology and Microbiology		
LC/MS-MS	Liquid Chromatography with Tandem Mass Spectrometry		
MedRA	Medical Dictionary for Regulatory Activities		
MFC	Minimum Fungicidal Concentration		
NIAID	National Institute of Allergy and Infectious Diseases		
NIH	National Institutes of Health		
OCRPRO	Office of Clinical Research Policy and Regulatory Operations		
OHRP	Office for Human Research Protections		
OMC	Onychomycosis		
OPC	Oropharyngeal Candidiasis		
PBMC	Peripheral blood mononuclear cell		
PI	Principal Investigator		
PK	Pharmacokinetic(s)		
PT	Prothrombin Time		
PTT	Partial Thromboplastin Time		
SAE	Serious Adverse Event/Serious Adverse Experience		

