7.4 Laboratory Evaluations

Stool, Saliva, and Vaginal Secretions

Stool, saliva, and vaginal secretions will be collected for PK analysis and may be used for other immunologic or microbiologic studies. Collection of stool and vaginal secretions is optional. Stool samples will be continuously collected (as available) for 24-hour PK analysis at the NIH Clinical Center on specified days. Saliva samples will be collected at pre-dose, 8 (± 3 hours) and 24 hours (± 1 hour) postdose for 24-hour PK analysis. Vaginal fluid will be collected by the

patient using the Instead™ Softcup (Evofem, Inc [San Diego, CA, USA]), a menstrual fluid collection device. The patient will insert the Softcup 24 hours postdose. After 2 hours, the patient will remove the cup and place it in a urine specimen container. There is a risk of dislodging an IUD with the Softcup; therefore, vaginal fluid collection will not be done in patients with IUDs. Vaginal fluid collection will be deferred during a patient's menstrual period and will not be done in patients who have had a hysterectomy with cervix removal.

In the study drug extension phase vaginal fluid will be collected by the subject using the Instead™ Softcup. The subject will insert the Softcup and remove it after 60 seconds and place it in a Falcon tube container. Vaginal collection is done unrelated to study drug administration time.

Urine

Urinalysis includes appearance, glucose, bilirubin, ketone, specific gravity, pH, protein, urobilinogen, nitrite, leukocyte esterase, white blood cell count, red blood cell count, hemoglobin.

Urine will also be continuously collected for 24-hour PK analysis on specified days.

Serum/Urine Pregnancy Test

A serum or urine pregnancy test will be given to women of childbearing potential as noted in the Study Schedule. Pregnancy prevention reminders and assessment of compliance will be done at each visit for subjects capable of becoming pregnant.

Blood Draws

Research evaluations on blood may include, but are not limited to, the following laboratory tests:

- PK
- Hematology: complete blood count with differential and platelet count
- Acute care panel, mineral panel, and hepatic panel

Plasma and PBMCs may be collected for storage. Plasma for 24-hour PK analysis (6 mL) will be collected in purple top K2-EDTA tubes at predose and 1 (± 5 minutes), 2 (± 5 minutes), 4 (± 15 minutes), 8 (± 15 minutes), Page 42 of 101

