8.1 Potential Risks

CAMB: There is limited experience in humans for the study drug. In the only clinical study on CAMB, side effects included nausea, abdominal pain, vomiting, and diarrhea. There was one instance of a moderate upper respiratory tract infection in a participant dosed with 800 mg of CAMB, but this was determined to not be related to CAMB. Risks associated with non-enchochleated formulations of AMB include nephrotoxicity, change in clotting factors, anemia, gastrointestinal intolerance, allergic reaction, or other unknown risks to this medication. These effects have not been observed in healthy humans dosed with CAMB. There is also the possibility that this treatment will have no effect on the fungal infection for which it is being used so the infection may worsen. It is possible that the Candida infecting or colonizing the study participant could become resistant to amphotericin due to the exposure to the study drug. This could limit treatment response to systemic intravenous amphotericin potentially in the future.

The effects of CAMB on the developing fetus are unknown. Therefore, patients must use appropriate and effective forms of contraception to avoid becoming pregnant or to avoid impregnating their partner.

Endoscopy and Biopsies: Diagnostic endoscopy when performed by a trained endoscopist is generally safe and well tolerated. Cardiopulmonary complications may account for over 50% of the reported complications, with the majority the result of aspiration, over-sedation, hypoventilation, vasovagal episodes, and airway obstruction. Significant complications can occur as a result of instrumentation, such as bleeding, perforation, and infection, with an overall frequency that approximates 0.1% for upper endoscopy. The risk of perforation and/or death is approximately 0.001%, but varies with the condition of the patient and performance of special procedures such as biopsy. These endoscopic complications were determined from elderly hospitalized patients, so the exact risk is unknown in the population for the current study.

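### The planned laboratory safety summary includes CRP, whose collection is not specified, and leaves out hemoglobin and other graded analytes drawn at every scheduled laboratory visit

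*Combined protocol and SAP*

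**What the plan says.** Section 13.3.2, under Clinical Laboratory Parameters, names what is summarised: "Clinical laboratory measurements (serum creatinine, potassium, CRP, ALT, AST"). The list closes after AST, and nothing marks it as a set of examples. For these measures, "changes from baseline to end-of-treatment will be summarized descriptively for each visit", using mean, median, SD, minimum and maximum.

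Section 7.4 describes the blood tests in open terms: "Research evaluations on blood may include, but are not limited to, the following" tests, which are PK, "Hematology: complete blood count with differential and platelet count", and "Acute care panel, mineral panel, and hepatic panel". The contents of the three panels are not itemised. Section 6.6 and Appendices B to E schedule the same hematology and panels. None of these places names CRP.

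On risk, section 8.1 states: "Risks associated with non-enchochleated formulations of AMB include nephrotoxicity, change in clotting factors, anemia, gastrointestinal intolerance", among others. Section 1.1.1 also names anemia as a limiting side effect of amphotericin B. Appendix A grades hemoglobin, neutrophils, platelets, ALP, bilirubin, magnesium and several other chemistries.

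**The concern.** The list and the collection schedule do not match, in two directions. One of the five analytes to be summarised has no stated collection. Most of the safety laboratory data that are collected have no planned summary, including the one that would show a toxicity the protocol itself names.

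Safety and tolerability are a secondary objective, and long-term safety up to 60 months is an exploratory one. With 16 patients (ceiling 20) and no control arm, the laboratory tables are the main way to see a slow drift that no single visit makes obvious. If the analytes are chosen after the open-label results are known, the choice of what to show is no longer prespecified.

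**Working it through.** **1. Listed analytes against scheduled collection.**

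| Analyte or group | In 13.3.2 list | Scheduled (7.4, 6.6, App. B–E) | Graded in App. A |
|---|---|---|---|
| Creatinine, potassium | yes | yes, taking them as panel members | yes |
| ALT, AST | yes | yes, taking them as panel members | yes |
| CRP | yes | not specified | no |
| Hemoglobin, neutrophils, platelets | no | yes (CBC, differential, platelets) | yes |
| ALP, total bilirubin | no | yes, taking them as panel members | yes |
| Magnesium, calcium, phosphate | no | only if the mineral panel reports them | yes |

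Of the five listed analytes, one has no specified collection and none is a hematology value. Neutrophils, bilirubin and ALP are also used for eligibility (4.3) and for entry to the extension (6.6).

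**2. Could a separate CRP sample be included in the Appendix C volumes?** The itemised volumes are hematology 3 mL, panels 4, pregnancy test 4, PK 48 (or 6 for a trough), and stored samples 10.

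- 200 mg/day path: screening 11 + Day 0 17 + Day 1 59 + Days 2, 4 and 7 at 7 each (21) + Day 14 69 + Day 21 7 + Day 28 27 + Day 42 7 = **218 mL** (stated: 218).
- 400 mg/day path: 177 through Day 14 + 21 (Days 15, 17, 20) + 69 (Day 27) + 7 + 27 + 7 = **308 mL** (stated: 308).
- 800 mg/day path: 267 through Day 27 + 21 (Days 28, 30, 33) + 69 (Day 40) + 7 + 27 + 7 = **398 mL** (stated: 398).

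The daily-volume row shows 11.5 mL at Day 20, but the cumulative row rises there by 198 − 191 = 7 mL, as the itemised volumes give. The totals therefore contain no separate CRP tube. They cannot exclude a CRP run on a tube already drawn.

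**3. How often hematology is drawn.** In Appendix C it is drawn at 10 of 10, 14 of 14 and 18 of 18 listed visits on the three paths. In Appendix E, weeks 2 to 258 in steps of two give 258/2 = 129 rows. Week 184 is absent, leaving 128. Check: one row of 23 mL, 22 of 27 mL and 105 of 7 mL give 23 + 594 + 735 = 1352 mL, the table's final total. Every row includes 3 mL for hematology, so 128 × 3 = 384 mL. That is the maximum for one patient who completes 60 months.

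**4. What the plan would show for a falling hemoglobin.** Take an illustrative patient who goes from 12 to 8.5 g/dL. Appendix A puts 8.0–9.4 g/dL at Grade 2, which is below the Grade 3 laboratory event named in the pausing criteria of 11.6. None of the five summarised analytes is hemoglobin, so no planned mean, change or range moves. The fall is reported only if it is recorded as an adverse event and reaches the MedDRA tables.

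**The case against.** The strongest reply is that anemia has a planned route into the report. Section 13.3.2 codes and tabulates adverse events by SOC and Preferred Term from first dose to the final visit. Section 11.2 counts laboratory reports as source documents. The appended Policy 801 treats an abnormal laboratory finding as an adverse event. This stands, so a reader who inferred that the plan has no table at all for anemia would be wrong. The route depends on someone recording the event, however. Section 11.2 enters only reportable events in the study database, and adverse event tables show no change from baseline and no grade shift.

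A reader might also infer that the CRP table will be empty. The documents do not show that. The test list in 7.4 is not exclusive, the panels are not itemised, and creatinine, potassium, ALT and AST are not named there individually either. What can be said is that CRP collection is not specified.

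The 384 mL could be read as blood drawn to no purpose. It is a one-patient maximum, and the counts also serve real-time safety decisions and can feed the adverse event tables.

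Three further points are fair. Section 8.1 attributes anemia to other amphotericin B formulations and says these effects have not been seen in healthy people given CAMB. The two laboratory-defined safety endpoints in 3.2.2, nephrotoxicity and hypokalemia, rest on creatinine and potassium, and both are on the list. Finally, "Vital signs will be summarized descriptively" in 13.3.2 without naming visits, which might suggest a second table with no source. The scheduled physical exams may supply those values, so this is missing detail only and no reason to drop that summary.

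**Conclusion.** The mismatch is real and limited to the safety reporting. The laboratory summary names one analyte whose collection is not specified, and omits every hematology value, bilirubin, ALP and any mineral analyte, although hematology and the panels are scheduled at every laboratory visit in the core study and the extension. Anemia would be visible only through adverse event recording.

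This reading takes the list in 13.3.2 as complete, as it is worded. It assumes that the panels report their usual members, which matters most for magnesium and the other mineral analytes because the documents do not itemise them. The 12 to 8.5 g/dL example is illustrative and is not a forecast. The primary endpoint, its decision rule and the two laboratory-defined safety endpoints are unaffected.

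**What to change.** In 13.3.2:

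- Extend the list to the scheduled safety analytes that Appendix A grades: at least hemoglobin, neutrophils, platelets, ALP and total bilirubin, plus magnesium and the other mineral and acute panel analytes if those panels report them. Keep creatinine, potassium, ALT and AST.
- Add one table of baseline grade against worst on-treatment grade by Appendix A, and state that it includes the extension.
- Remove CRP from the list unless it was in fact measured. If it was, say at which visits.
- Keep the vital-signs summary.

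This needs no new blood, visits or clinical rules. The cost is a few more descriptive tables and some data work. Extension results may come from local laboratories as copies sent to the investigator (6.6), so those values must be entered, and Appendix A has them graded against each laboratory's own reference limits where these differ.

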13.3.3 PK Analysis

Plasma drug levels will be determined predose and at 1 (± 5 minutes), 2 (± 5 minutes), 4 (± 15 minutes), 8 (± 15 minutes), 10 (± 15 minutes), 12 (± 15 minutes), and 24 hours (± 1 hour) postdose on Days 1 and 14 (all dosages), 21 (200 mg/day), 27 (400 and 800 mg/day), and 40 (800 mg/day). Blood samples will be processed to measure plasma concentrations via a validated LC-MS/MS assay. Twenty-four-hour urine collections will have total volume recorded and a 10-mL sample aliquoted to measure concentrations via a validated LC-MS/MS assay. Saliva collected at predose and at 8

(±3 hours) and 24 (±1 hours) hours postdose on Days 1 and 14 (± 3 days) of each dosage level will be analyzed to measure concentrations via LC-MS/MS assay. Stool samples will be collected during the 24 hours after the initial dose, and at Day 14 (± 3 days) days of each dosage. Vaginal secretions will be collected between 24-26 hours postdose on Days 1 and 14 (± 3 days) of each dosage level and will

Blood, stool, urine and saliva samples will be analyzed by Lambda Therapeutic Research Inc. ([name]) CAMB plasma PK parameters will be determined using noncompartmental methods with Phoenix® WinNonlin® software (version 6.03; Pharsight Corporation, Mountain View, CA). Maximum plasma concentration (C_{max}) and time to reach C_{max} (T_{max}) will be obtained directly by observation of the plasma concentration vs. time profiles. The apparent elimination rate constant (λZ) will be determined by calculating the absolute value of the slope of the log-linear regression of at least 2 points of the plasma concentration—time plot (when reported). The elimination half-life ($T_{1/2}$) will be calculated as 0.693/ λ Z (when reported). The steady-state area under the concentration vs. time curve (AUC) from time 0 to 24 hours postdose (AUC₀₋₂₄) will be calculated using the linear (up)/logarithmic (down) trapezoidal rule with a minimum of four quantifiable concentrations. Dose proportionality (linearity) will be assessed by comparison of geometric means of AUC and C_{max} PK parameters among dose levels. The percentage of total administered dose excreted in urine will be determined and used to calculate the renal elimination rate constant and renal clearance. Saliva levels will be reported as descriptive data.

be analyzed to measure concentrations via LC-MS/MS assay. The stool and

vaginal samples will be optional for subjects.

14 Ethics/Protection of Human Subjects

